#### **6.4.4. Markers of Complement Activation, Inflammation and Renal Injury**

Samples for measurement of markers of complement activation, inflammation and renal injury will be collected at the time points outlined in the Schedule of Assessments ([Table 1](#)) and analyzed by central laboratories. On dosing days, blood samples will be collected predose.

### **6.5. Pharmacodynamic Assessments**

Blood samples for PD analysis will be collected at the time points outlined in the Schedule of Assessments ([Table 1](#)). Samples will be collected prior to administration of cemdisiran or placebo on dosing days.

Analysis of PD will include the impact of cemdisiran administration on plasma C5 protein levels (assessed by a mass spectrometry-based method) and serum complement activity (assessed by CAP enzyme linked immunosorbent assay [ELISA] and CCP ELISA). Samples will be analyzed at central laboratories. Details regarding the collection, processing, shipping, and storage of the samples will be provided in the Laboratory Manual.

### **6.6. Pharmacokinetic Assessments**

Blood samples and urine samples will be collected for assessment of cemdisiran PK parameters and possible metabolite analysis at the time points in the Schedule of Assessments. A detailed schedule of time points for the collection of blood samples and urine samples for PK analysis is in [Table 3](#).

The concentration of cemdisiran will be determined using a validated assay. Details regarding sample volumes to be collected, and the processing, shipping, and analysis of the samples will be provided in the Laboratory Manual.

## 6.7. Safety Assessments

The assessment of safety during the study will consist of the surveillance and recording of the frequency of AEs including SAEs, recording of concomitant medication and measurements of vital signs, weight and height, physical examination, and ECG findings and laboratory tests, including assessment of IgG/IgM/IgA ADA and CIC. Clinically significant abnormalities observed during the physical examination are recorded.

Safety will be monitored over the course of the study by a DMC as described in Section 3.7.

### 6.7.1. Vital Signs

Vital signs will be measured as specified in the Schedule of Assessments ([Table 1](#) and [Table 2](#)) and include blood pressure, heart rate, body temperature, and respiratory rate. Vital signs will be measured in the seated or supine position, after the patient has rested comfortably for 10 minutes. On Day 1, vital signs will be collected at predose and 4 hours ( $\pm 15$  minutes) postdose. On all other dosing days, vital signs will be collected predose.

Blood pressure should be taken using the same arm throughout the study. Body temperature in degrees Celsius will be obtained via oral or tympanic method. Heart rate will be counted for a full minute and recorded in beats per minute, and respiration rate will be counted for a full minute and recorded in breaths per minute.

Additional vital sign assessments, as medically indicated, may be added at the discretion of the Investigator, or as per DMC advice.

Vital signs results will be recorded in the eCRF.

### 6.7.2. Weight and Height

Height will be measured in centimeters. Body weight will be measured in kilograms. Height and body weight measurements will be collected as specified in the Schedule of Assessments ([Table 1](#) and [Table 2](#); height at Screening only and dosing weight during the clinical study center visits) and will be recorded in the eCRF.

### 6.7.3. Physical Examination

Routine physical examinations will be conducted according to the Schedule of Assessments ([Table 1](#) and [Table 2](#)); if a physical examination is scheduled for a dosing visit, it should be conducted prior to dosing.

At Screening and Day 1 predose, a full physical examination will be performed. At all other time points, including Day 1 at 4 hours ( $\pm 30$  minutes) postdose, a directed physical examination will be performed.

Full physical examinations will include the examination of the following: general appearance; head, eyes, ears, nose and throat; respiratory, cardiovascular, gastrointestinal, musculoskeletal, and dermatological systems; thyroid; lymph nodes; and neurological status.

Directed physical examinations will include examination of the following: respiratory, cardiovascular, dermatological, gastrointestinal, and musculoskeletal systems.

Clinically significant abnormalities observed during the physical examination are recorded on the medical history or AE eCRF.

#### **6.7.4.      Electrocardiogram**

Twelve-lead ECGs reporting rhythm, ventricular rate, RR interval, PR interval, QRS duration, and QT interval and Fridericia-corrected QT interval will be obtained, as specified in the Schedule of Assessments ([Table 1](#) and [Table 2](#)). Patients should be supine for at least 5 minutes before each ECG is obtained. A single 12-lead ECG will be performed at Screening. At all other time points, 12-lead ECGs will be performed in triplicate, with readings approximately 1 minute apart. 12-lead ECGs will be performed at predose; 60 minutes postdose; and 4 hours postdose in relation to the Day 1 and Week 32 cemdisiran or placebo doses.

When ECG and blood sample collection occur at the same time, ECGs should be performed before blood samples are drawn.

The Investigator or qualified designee will review all ECGs to assess whether the results have changed since the Baseline visit and to determine the clinical significance of the results. These assessments will be recorded on the eCRF. Additional ECGs may be collected at the discretion of the Investigator, or as per DMC advice.

#### **6.7.5.      Clinical Laboratory Assessments**

The following clinical laboratory tests will be evaluated by a central laboratory. However, to assess patient eligibility at the end of the run-in period, eGFR will also be assessed locally. Specific instructions for transaminase elevations are provided in [Section 5.2.3.1](#). For any other unexplained clinically relevant abnormal laboratory test occurring after study drug administration, the test should be repeated and followed up at the discretion of the Investigator, or as per DMC advice, until it has returned to the normal range or stabilized, and/or a diagnosis is made to adequately explain the abnormality. Additional safety laboratories and assessments as indicated by the clinical situation may be requested. Clinical laboratory assessments are listed in [Table 5](#) and include: hematology, serum chemistry and urinalysis parameters. Parameters will be assessed as specified in the Schedule of Assessments ([Table 1](#) and [Table 2](#)).

While local laboratory results may be used for urgent clinical and dosing decisions, on the day of the clinic visit assessments, all laboratory assessments specified in [Table 5](#) which are performed at the clinic should also be sent in parallel to the central laboratory. In the case of discrepant local and central laboratory results on samples drawn on the same day, central laboratory results will be relied upon for clinical and dosing decisions.

Clinical laboratory assessments may be collected at the clinical study center or at home by a trained healthcare professional. On dosing days blood samples will be collected predose.

For any safety event or laboratory abnormality, additional laboratory assessments, imaging, and consultation may be performed for clinical evaluation and/or in consultation with the Medical Monitor; results may be collected and should be included in the clinical database.

**Table 5: Clinical Laboratory Assessments**

Hematology	
Complete blood count with differential	
Serum Chemistry	
Sodium	Potassium
BUN	Phosphate
Creatinine and eGFR (using the CKD-EPI formula)	Albumin
Uric acid	Calcium
Total protein	Carbon dioxide
Glucose	Chloride
Liver Function Tests	
AST	ALP
ALT	Bilirubin (total and direct)
GGT	
Urinalysis	
Visual inspection for appearance and color	Bilirubin
pH	Nitrite
Specific gravity	RBCs
Ketones	Urobilinogen
Albumin	Leukocytes
Glucose	Microscopy
Protein	
Coagulation	
Prothrombin time	International Normalized Ratio
Partial Thromboplastin Time	
Immunogenicity (see Section 6.7.5.1)	
Antidrug antibodies	
Hepatic Tests (Screening Only)	
Hepatitis C, including: HCV RNA PCR – qualitative and quantitative assays	Hepatitis B, including: HBs Ag, HBc antibody IgM and IgG
Pregnancy Testing (Females of Child-bearing Potential Only) (see Section 6.7.5.2)	
$\beta$ -human chorionic gonadotropin	

Abbreviations: ALP=alkaline phosphatase; ALT=alanine transaminase; AST=aspartate transaminase; BUN=blood urea nitrogen; CKD-EPI=Chronic Kidney Disease Epidemiology Collaboration; eGFR=estimated glomerular

filtration rate; GGT=gamma glutamyl transferase; HAV=hepatitis A virus; HBsAg=hepatitis B virus surface antigen; HBc=hepatitis B virus core; HCV=hepatitis C virus; IgG= IgG=immunoglobulin G antibody; IgM=immunoglobulin M antibody; PCR=polymerase chain reaction; RBC=red blood cell; RNA=ribonucleic acid.

#### **6.7.5.1. Immunogenicity**

Blood samples will be collected to evaluate ADA and CIC. IgG/IgM/IgA ADA to total drug will be assessed at Screening and during the study. ADA samples will be tested in real time. Clinical study decision will be based on confirmed positive ADA results from the IgG/IgM/IgA assay. Confirmed positive ADA samples will be further characterized for cemdisiran domain specificity against the Tri-GalNAc component if a reliable method is established. Blood samples for ADA and CIC testing must be collected before study drug administration as specified in the Schedule of Assessments ([Table 1](#) and [Table 2](#)). Blood samples to evaluate ADAs will be collected at Screening to assess study eligibility and at the Early Termination (ET) visit, if applicable. ADA and CIC will be routinely monitored during the treatment period and throughout the open-label extension phase and safety follow up, as indicated in the Schedule of Assessments. Finally, ADA and CIC samples will also be collected and analyses will be performed and prioritized if any clinical evidence of progression of IgAN disease and/or relevant safety findings. Patients who are confirmed positive for IgG/IgM/IgA ADA at baseline will be excluded from study treatment. In addition, patients who develop de novo ADAs will be discontinued from study drug but will be followed until EOS visit and during safety follow up. These patients will also be monitored until ADA levels return to baseline.

Exploratory analysis of anti-Gd-IgA1 antibody levels will be conducted; serum samples for these analyses will be drawn when CIC samples are collected.

Details regarding the processing, shipping, and analysis of the samples will be provided in the Laboratory Manual.

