Study Drug Administration	5.2.2									X	X	X	X	X	X	X	X	X	X	X																
24-hours Urine Proteinuria Assessment (from 2 valid collections)	6.4.1.1								X																											

Study Visit (Day/Week)	Notes For details, see Section	Screening		Run-in Period (14 weeks)		Treatment Period (36 weeks)								Safety Follow up						
		D-189 to D-99	D-112 ±7 Screening visit	D-98 ±7 Week -14	D-56 ±7 Week -8	D-14 ±3 Week -2	D1	Day 1	D28 ±3 Week 4	D56 ±3 Week 8	D84 ±3 Week 12	D112 ±3 Week 16	D140 ±3 Week 20	D168 ±3 Week 24	D196 ±3 Week 28	D224 ±3 Week 32 (EOT)	D252 ±3 Week 36 (EOS/ET)	D343 ±14 Week 49	D434 ±14 Week 62	D525 ±14 Week 75
24-hours Urine Proteinuria Assessment (from a single valid collection)	6.4.1.1		X									X						X		X
CAP/CCP Blood Sample	6.5							X	X	X	X	X	X	X	X	X	X	X	X	X
C5 Levels Blood Sample	6.5							X	X	X	X	X	X	X	X	X	X	X	X	X
eGFR Calculation	6.4.3		X	X	X	X	X	X	X	X	X	X	X	X	X	X	X	X	X	X
Urine Sample for Urinalysis and Microscopy	6.4.2 and 6.7.5		X	X	X	X	X	X	X	X	X	X	X	X	X	X	X	X	X	X
Spot Urine for Albumin, Protein and Creatinine	6.4.1.2		X	X	X	X	X	X	X	X	X	X	X	X	X	X	X	X	X	X
Blood Sample for Antidrug Antibodies	6.7.5.1		X					X	X		X			X		X	X	X	X	X
Blood Sample for CIC Analysis and Exploratory Gd-IgA1 Assessment	6.7.5.1		X					X	X		X			X		X				
Optional Blood Sample for B-cell function Analysis	6.7.5.1		X																	
Exploratory Blood Sample	6.4.4						X		X		X		X		X					

Study Visit (Day/Week)	Notes For details, see Section	Screening		Run-in Period (14 weeks)		Treatment Period (36 weeks)								Safety Follow up																							
		D-189 to D-99	Screening visit	D-112 ±7	Week -14	D-98 ±7	Week -14	D-56 ±7	Week -8	D-14 ±3	Week -2	D1	Day 1	D28 ±3	Week 4	D56 ±3	Week 8	D84 ±3	Week 12	D112 ±3	Week 16	D140 ±3	Week 20	D168 ±3	Week 24	D196 ±3	Week 28	D224 ±3	Week 32 (EOT)	D252±3	Week 36 (EOS/ET)	D343±14	Week 49	D434±14	Week 62	D525±14	Week 75
Blood Sample for Exploratory Genetic Analysis	6.8.											X																									
Exploratory Urine Sample	6.4.4.											X		X		X		X		X																	
Plasma and Urine PK	See Table 3											X																									
Optional Home Visit	Will be arranged where feasible during safety follow up at Weeks 49 and 75																															X					
Adverse Events	6.7.6.2																																	X			
Concomitant Medications	5.3	X	X																															X			

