Antibiotics Compliance (if applicable)	5.5.3																																		X		
IgAN standard of Care Compliance																																			X		

Table 2: Schedule of Assessments – Open-Label Extension Period and Safety Follow up

Study Visit (Day/Week)	Notes For details, see Section	Open-Label Extension Period (52 weeks)												Safety Follow up																			
		D252 ±7	Week 36	D280 ±7	Week 40	D308 ±7	Week 44	D336 ±7	Week 48	D364 ±7	Week 52	D392 ±7	Week 56	D420 ±7	Week 60	D448 ±7	Week 64	D476 ±7	Week 68	D504 ±7	Week 72	D532 ±7	Week 76	D560 ±7	Week 80 (OLE EOT)	D588 ±7	Week 84 (OLE EOSET)	D679 ±14	Week 97	D770 ±14	Week 110	D861±14	Week 123
Routine Physical Exam	6.7.3									X						X				X		X			X			X					
Height, Weight and BMI	6.7.2									X						X				X		X			X			X					
Vital Signs	6.7.1	X	X	X	X	X	X	X	X	X	X	X	X	X	X	X	X	X	X	X	X	X	X	X	X	X	X	X	X				
12-Lead ECG	6.7.4								X											X	X				X			X					
Clinical Laboratory Assessment	6.7.5	X	X			X				X			X			X			X		X	X	X	X	X	X	X	X	X	X			
Pregnancy Test	6.7.5.2	X	X			X			X			X			X			X		X	X	X	X	X	X	X	X	X	X	X			
Study Drug Administration	5.2.2	X	X	X	X	X	X	X	X	X	X	X	X	X	X	X	X	X	X	X													
24-hours Urine Proteinuria Assessment (from 2 valid collections)	6.4.1.1																						X										
24-hours Urine Proteinuria Assessment (from a single valid collection)	6.4.1.1									X							X								X			X					
CAP/CCP Blood Sample	6.5	X	X			X			X			X			X		X		X		X	X	X	X	X	X	X	X	X	X			
C5 Levels Blood Sample	6.5	X	X			X			X			X			X		X		X		X	X	X	X	X	X	X	X	X	X			
eGFR Calculation	6.4.3	X	X			X			X			X			X		X		X		X	X	X	X	X	X	X	X	X	X			

Study Visit (Day/Week)	Notes For details, see Section	Open-Label Extension Period (52 weeks)												Safety Follow up			
		Week 36	Week 40	Week 44	Week 48	Week 52	Week 56	Week 60	Week 64	Week 68	Week 72	Week 76	Week 80 (OLE EOT)	Week 84 (OLE EOS/ET)	Week 97	Week 110	Week 123
Urine Sample for Urinalysis and Microscopy	6.4.2 and 6.7.5	X	X		X		X		X		X		X	X	X	X	X
Spot Urine for Albumin, Protein and Creatinine	6.4.1.2	X	X		X		X		X		X		X	X	X	X	X
Blood Sample for Antidrug Antibodies	6.7.5.1				X						X			X	X	X	X
Exploratory Blood Sample	6.4.4		X		X		X		X		X		X	X			
Exploratory Urine Sample	6.4.4		X		X		X		X		X		X	X			

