### 6.7.5.1. Immunogenicity

Blood samples will be collected to evaluate ADA and CIC. IgG/IgM/IgA ADA to total drug will be assessed at screening and during the study. ADA samples will be tested in real time. Clinical study decision will be based on confirmed positive ADA results from the IgG/IgM/IgA assay. Confirmed positive ADA samples will be further characterized for cemdisiran domain specificity against the Tri-GalNAc component if a reliable method is established. Blood samples for ADA and CIC testing must be collected before study drug administration as specified in the Schedule of Assessments ([Table 1](#) and [Table 2](#)). Blood samples to evaluate ADAs will be collected at Screening to assess study eligibility and at the Early Termination (ET) visit, if applicable. ADA and CIC will be routinely monitored during the treatment period and throughout the open-label extension phase and safety follow up, as indicated in the Schedule of Assessments. Finally, ADA and CIC samples will also be collected and analyses will be performed and prioritized if any clinical evidence of progression of IgAN disease and/or relevant safety findings. Patients who are confirmed positive for IgG/IgM/IgA ADA at baseline will be excluded from study treatment. In addition, patients who develop de novo ADAs will be discontinued from study drug but will be followed until EOS visit and during safety follow up. These patients will also be monitored until ADA levels return to baseline.

Exploratory analysis of Gd-IgA1 levels and IgA-containing immune complexes may be conducted; blood samples for these analyses will be drawn when CIC samples are collected to enable these assays.

For US patients only, an optional blood sample may be collected at screening to evaluate any potential for B-cell stimulation by cemdisiran, at the Sponsor's discretion.

Details regarding the processing, shipping, and analysis of the samples will be provided in the Laboratory Manual.

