  - An independent DMC will perform regular reviews of safety, tolerability, and immunogenicity data throughout the study with the primary purpose of protecting the safety of participating patients and the integrity of the study. The DMC will operate under the rules of a Charter that will be reviewed and approved at the organizational meeting of the DMC. The DMC will perform periodic reviews of unblinded data (safety, tolerability, PK, pharmacodynamics (PD), ADA, CIC and efficacy of cemdisiran) during the clinical trial, and on an ad hoc basis review emergent safety data. Details are provided in the DMC Charter.
- Schedule of Assessments:
  - Added more time points for blood sample collection for the analysis of ADAs (Table 1 and Table 2)
    - “X” was added to “Blood Sample for Antidrug Antibodies” at the Screening visit, Week 36 and Safety Follow up visits at Weeks 49, 62, 75, 88 (Table 1); and Weeks 97, 110, 123, 136 (Table 2)
  - Added time points for blood sample collection for the analysis of CIC (Table 1)
    - A new row was added for the collection of blood samples for circulating immune complexes at all timepoints where ADA samples are collected. During the Treatment Period (Table 1), “X” was added at the Screening visit, Day 1 and at Weeks 4, 8, 12, 24 and 32.

- Added a time point for an optional blood sample collection for B-cell function analysis (Table 1)
  - A new row was added for an optional collection of blood samples for B-cell function analysis. During the Treatment Period (Table 1), “X” was added at the Screening visit.
- Section 4.2 (Exclusion Criteria): Updated to include a risk mitigation measure for ADA (excluding patients with confirmed positive IgG/IgM/IgA ADA at screening)
  - New Criterion 7: **Confirmed positive IgG/IgM/IgA ADAs to cemdisiran at Screening**
- Sections 6.1, 6.3 and 6.7: Updated to include the assessment of ADA and/or CIC.
  - Section 6.1 (Screening Assessments)
    - Additional screening assessments include a full physical examination (with emphasis on presence/degree of edema), collection of vital signs, height, weight and body mass index (BMI), 12-lead electrocardiogram (ECG), clinical laboratory assessments, pregnancy, 24-hours urine proteinuria assessment (from a single valid collection; see Section 6.4.1.1), eGFR, and urinalysis **and ADA and CIC assessments**.
  - Section 6.3 (Baseline Assessments – Treatment Period)

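### Section 6.7.5.1 promises routine circulating immune complex (CIC) monitoring through the open-label extension and safety follow-up, but Amendment 1's Table 2 has no CIC row; Amendment 2 repeats the promise, and its Table 2 needs checking

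*Protocol*

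**What the plan says.** - **Body text.** Section 6.7.5.1 (Immunogenicity) states, identically in Amendments 1 and 2 and for ADA as well: "CIC will be routinely monitored during the treatment period and throughout the open-label extension phase and safety follow up, as indicated in the Schedule". It thus defers to the schedule for the visits. A sentence just before it says "Blood samples for ADA and CIC testing must be collected before study drug administration as specified in the Schedule of Assessments" and points to both Table 1 and Table 2. Event-driven ADA and CIC sampling, on disease progression or a relevant safety finding, is a separate provision. The exploratory Gd-IgA1 work uses samples drawn when CIC is drawn; in Amendment 2 this is anti-Gd-IgA1 antibody.
- **Amendment 1 schedule.** Table 1 has a row "Blood Sample for CIC Analysis and Exploratory Gd-IgA1 Assessment". The later periods are in "Table 2: Schedule of Assessments – Open-Label Extension Period and Safety Follow up", which has rows for ADA, exploratory blood and exploratory urine, and none for CIC.
- **Amendment 1 change log.** It says the new CIC row applies wherever ADA is sampled. It then says that, for the treatment period in Table 1, a mark "was added at the Screening visit, Day 1 and at Weeks 4, 8, 12, 24 and 32". It names Table 1 alone for CIC, and both tables for ADA.
- **Amendment 2 change log.** The CIC clarification is placed in Table 1, Screening through Week 36. The only change listed for Table 2 is to laboratory and pregnancy tests.

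**The concern.** The sentence makes a monitoring commitment and leaves the visits to the schedule. If the schedule lists no CIC sample in the OLE or follow-up, sites will follow the table and the monitoring will not take place.

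CIC is tied to a risk specific to this disease. Section 1.5 names a theoretical risk that the GalNAc moiety could stimulate pathogenic autoantibodies and immune complexes. Section 6.7 lists CIC among the safety assessments, and Section 3.7 lists it among the data the DMC reviews. The rationale for Amendment 2 says OLE safety assessments should mirror those at initial treatment, because placebo patients are first exposed there. These are the patients for whom a routine CIC sample would be missing.

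**Working it through.** No figure in the protocol needs reproducing. The check sets text against schedule, then counts visits.

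**Amendment 1, routine visits after Screening.** Week 88 and Week 136 are ADA visits taken from the change log, because those columns are not legible in the tables.

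| Period | ADA | CIC |
|---|---|---|
| Treatment (Table 1) | Day 1, Weeks 4, 12, 24, 32, 36 | Day 1, Weeks 4, 12, 24, 32 |
| Follow-up without OLE (Table 1) | Weeks 49, 62, 75, 88 | none marked |
| OLE (Table 2) | Weeks 48, 72, 84 | no row |
| Follow-up after OLE (Table 2) | Weeks 97, 110, 123, 136 | no row |

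The two rows agree through Week 32 and diverge afterwards. The finding rests on the missing Table 2 row. The blank cells at the end of the Table 1 CIC row agree with it, but that table is damaged in extraction and should not carry the argument. Displaced cells cannot remove a whole row, and the log's naming of Table 1 alone for CIC points the same way.

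**Patients affected.** Section 3.1 plans 10 placebo patients and places the first OLE dose at Week 36. If all of them enter the optional OLE, about 10 patients are first exposed at Week 36.

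**Time without a routine sample.** From first dose to last follow-up is 136 − 36 = 100 weeks. Over that time:
- CIC draws: 0.
- ADA draws: 3 (Weeks 48, 72, 84) + 4 (Weeks 97, 110, 123, 136) = 7.

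**Comparison.** Patients randomised to cemdisiran have 4 on-drug CIC samples in their first 32 weeks by the Table 1 row (Weeks 4, 12, 24, 32), or 5 by the log, which adds Week 8.

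**Amendment 2.** The sentence is unchanged and its log adds no CIC visit to Table 2. If its Table 1 does mark CIC at Week 36, Section 6.7.5.1 requires collection before dosing, so that sample would still precede a placebo patient's first cemdisiran dose.

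**The case against.** Several points on the other side have weight.

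1. A reader might infer that the Amendment 1 log itself ends CIC sampling at Week 32. It does not say so. The list stopping at Week 32 is introduced as the treatment-period list for Table 1, and the sentence before it applies CIC to every ADA visit. The log is not consistent with itself, and it also lists a Week 8 that the extracted row lacks. It cannot prove that CIC stops. It does show that parity with ADA was intended, which Table 2 does not provide.

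2. A reader might infer that the protocol in force is shown to be wrong. It is not, because Amendment 2's tables are not in the text available. Its log says administrative changes since Amendment 1 are not detailed and that only primary sections are indicated. Its stated aim of mirroring initial-treatment safety assessments in the OLE also makes silence a less secure guide. This objection stands, and limits the current-version claim to an inference.

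3. A reader might infer that the immune-complex risk goes unmonitored in the OLE. That is too strong. ADA remains scheduled, dosing decisions rest on confirmed ADA, and event-driven CIC sampling continues. CIC and anti-Gd-IgA1 results are only summarised descriptively.

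4. The deferral to the schedule might seem to remove the conflict. It does not: the sentence promises monitoring throughout two periods for which Amendment 1's Table 2 lists no CIC sample.

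**Conclusion.** Within Amendment 1 the inconsistency is established: routine CIC monitoring is promised for the OLE and safety follow-up, and Table 2 schedules none. For Amendment 2 it is a well-supported inference from the unchanged sentence and a log with no CIC change to Table 2.

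The consequence is modest and concerns safety data only. On this schedule up to about 10 patients would have 0 routine CIC or anti-Gd-IgA1 samples over the 100 weeks after first exposure. This assumes that all placebo patients enter the OLE and complete follow-up, and that the Table 2 in force matches Amendment 1 on this point. No efficacy endpoint or primary analysis is touched. The correction is worthwhile because CIC bears directly on the named risk and the DMC is meant to see it.

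**What to change.** First check the Table 2 in force. If it already has a CIC row covering the OLE and follow-up, no Table 2 change is needed. If not:

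- Add a row for CIC and anti-Gd-IgA1 to Table 2 at the existing ADA draws: Weeks 48, 72, 84, 97, 110, 123 and 136.
- Add matching marks to the Table 1 CIC row at Weeks 36, 49, 62, 75 and 88, for patients who do not enter the OLE.

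**Cost.** No new visits; one extra tube and assay where blood is already drawn. For ex-placebo patients this is 7 × 10 = 70 collections. If all randomised patients enter the OLE, it is at most 7 × 30 = 210. Each patient who does not enter adds 5.

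**Optional.** A Week 40 sample would fall 40 − 36 = 4 weeks after first exposure and mirror the Week 4 sample. Week 40 is already a clinic visit with an exploratory blood draw. It goes beyond reconciling text and table and adds one collection per OLE patient (10 ex-placebo, at most 30).

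Limiting the sentence to ADA after Week 32, while keeping event-driven CIC sampling, would also remove the contradiction at no sampling cost. It would add no monitoring of the named risk, so it is the weaker choice.
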